## 8.2 SAFETY PARAMETERS

All ocular adverse events (device related and unrelated) and all Secondary Surgical Interventions (SSIs) of the study eyes during the conduct of the study will be presented.

### 8.2.1 ADDITIONAL SAFETY ANALYSES

The safety outcomes will be summarized descriptively for all eyes that have the procedure attempted.

#### BCDVA

BCDVA will be presented with the number and percent of eyes who fall into each category of BCDVA at each visit (e.g. 20/20 or better, 20/25 or better, 20/32 or better, etc.). The mean BCDVA letter score will be calculated for each visit. Change in BCDVA from Postop Week 3 or from Preoperative will be presented at each visit as categorical outcomes of “Increase in 15 letters or more”, “Increase in 10-14 letters”, “Increase in 5-9 letters”, “No change”, “Decrease in 5-9 letters”, “Decrease in 10-14 letters”, and “Decrease in 15 letters or more”.

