### 6.1 INCLUSION CRITERIA

- Must sign a written Informed Consent form and be willing to undergo cataract surgery for unilateral or bilateral implantation of the RxLAL.
- Between the ages of 40 and 80 inclusive on the day the cataract surgery is performed.
- Study eye must have preoperative keratometric cylinder of  $\geq 0.50$  D and  $\leq 3.00$  D.
- Study eye must have cataract causing reduction in best corrected distance visual acuity (BCDVA) to a level of 20/32 or worse with or without a glare source.
- Study eye must have best corrected distance visual acuity projected (by clinical estimate based upon past ocular history or retinal exam) to be 20/20 or better after cataract removal and IOL implantation.
- If only one subject eye is enrolled in the study, the non-study eye must have potential for BCDVA of 20/40 or better after cataract removal and IOL implantation.
- Study eye has clear intraocular media other than cataract.
- Willing and able to comply with the requirements for study specific procedures and visits.
- Study eye has a dilated pupil diameter of  $\geq 7.0$  mm.
- Study eye requires an IOL power within the range available for the RxLAL.

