#### **7.3.2.1 Postponement of Light Treatment Procedure(s)**

LDD treatment should be delayed if any of the following new symptoms or changes in performance are noted;

- [REDACTED]
- [REDACTED]
- Best Corrected Distance Visual Acuity: With any loss of BCDVA (unless the cause is known to be non-retinal) of 10 letters or more on an ETDRS (logMAR) chart, treatment should be delayed.

[REDACTED]

- If sutures were utilized at the time of surgery to close the incision wound, light treatments should not commence on the study eye until a minimum of 4 weeks after suture removal.
- A study eye with an ocular adverse event that could be negatively impacted by light treatment or negatively impact the effectiveness or safety of a light treatment should have light treatments delayed until after the adverse event has subsided. This includes corneal edema and superficial punctate keratitis (SPK) (Grade 3 (moderate) or more severe)), retinal conditions including diabetic retinopathy and cystoid macular edema, epithelial defect, and endophthalmitis.
- If a study eye is discovered with evidence of premature photopolymerization as evidenced as a zone on the lens surface, the investigator should contact the Sponsor for further instructions. (see [REDACTED] for additional details regarding premature photopolymerization).
- Any study eye possessing clinically significant posterior capsular (PC) haze should undergo a YAG capsulotomy procedure prior to the adjustment. A minimum of 48 hours should separate the YAG treatment from the corresponding refraction and LDD adjustment.

---

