### 7.3.2.2 Procedure Preparation

Protocol-required measurements should be completed prior to adjustment or lock-in treatments.

The subject should be prepared for light treatments as follows:

1. The study eye will be dilated using any of the following pupil dilation drops [REDACTED] or pupil [REDACTED] dilation gel [REDACTED]. After waiting an appropriate amount of time for dilation to occur, the study eye will be examined to ensure that adequate dilation (enough of the edge of the RxLAL optic can be visualized to allow for centration during LDD light treatment) has been obtained. If adequate dilation has not been obtained, additional dilating drops with manual punctal occlusion or a sponge soaked in mydriatic medication and applied to the ocular surface can be utilized to try and gain further dilation. If adequate pupil dilation is still not achieved with the methods described above, the treatment will be rescheduled and the dilation attempted at another visit.
2. Once adequate pupil dilation is achieved, the subject's fellow eye will be patched and the subject will be comfortably positioned in front of the LDD with chin in the chinrest and forehead against the support bar. The subject is asked to grasp the handles on the LDD for support and is asked to look straight ahead and concentrate on the green fixation light presented in front of them and to try to minimize eye movement.

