#### 7.4 EXAMINATION SCHEDULE

Subjects who agree to participate in the study will return for the listed follow-up examinations for each study eye:

Evaluation	
Preoperative	Day -90 to Day -1
Operative	Day 0, day of surgery
Postop Day 1	Days 1 to 2 postop
Postop Week 1	Days 7 to 14 postop
Postop Week 3	Days 17 to 24 postop: Adjustment #1
Adjustment #2, if needed	3 to 7 days post Adjustment #1
Adjustment #3, if needed	3 to 7 days post Adjustment #2
Lock-in #1	3 to 7 days post final adjustment
Lock-in #2, if needed	3 to 7 days post lock-in #1
Post Lock-In	3 to 7 days post final lock-in
1 Month Post Lock-In	30 to 60 days post final lock-in
3 Months Post Lock-In/6 Months Postop	Days 120 to 180 postop

Unscheduled visits falling outside the designated ranges for scheduled visits will be considered “interim” visits for data recording purposes and a report form will be completed.

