## 8 STATISTICAL METHODS

### 8.1 POPULATIONS FOR ANALYSIS

Exploratory effectiveness analyses will be performed on observed data for all primary eyes, fellow eyes, and all eyes successfully implanted with the RxLAL.

Safety analyses will be performed on observed data for all eyes of subjects who sign the informed consent and the procedure was attempted which is defined as the point at which the RxLAL makes contact with the eye. No imputation will be performed.

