##### UCDVA

Number and percent of primary eyes, fellow eyes, and all eyes (i.e. primary and fellow eyes) successfully implanted with the RxLAL with a UCDVA of 20/20 or better at 6 Months Postop (3 Months Post Lock-In) will be presented and the corresponding 95% confidence interval for the percent based on the binomial distribution will be calculated.

UCDVA will be presented with the number and percent of eyes that fall into each category of UCDVA (e.g. 20/20 or better, 20/25 or better, 20/32 or better, etc.) at each visit. The mean UCDVA letter score will be calculated for each visit. Change in UCDVA from Postop Week 3 will be presented at each visit as categorical outcomes of “increase in 15 letters or more”, “Increase in 10-14 letters”, “Increase in 5-9 letters”, “No change”, “Decrease in 5-9 letters”, “Decrease in 10-14 letters”, and “Decrease in 15 letters or more”. The mean change from Postop Week 3 will also be presented.

UCDVA will also be presented with the number and percent of eyes that fall into each category of UCDVA (e.g. 20/20 or better, 20/25 or better, 20/32 or better, etc.) stratified into two bins based on preoperative keratometric cylinder ( $\geq 0.50$  D and  $\leq 1.50$  D) and ( $> 1.50$  D and  $\leq 3.00$  D). The mean UCDVA letter score will be calculated for each of the two defined preoperative keratometric cylinder bins.

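### Does leaving the BCDVA change table open between a Postop Week 3 and a Preoperative reference hide vision loss after light treatment?

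*Combined protocol and SAP*

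**What the plan says.** Section 8.2.1 (BCDVA) promises three outputs: the number and percent of eyes in each acuity category at each visit, the mean letter score at each visit, and a table of letter change in seven bands. On the third it says "Change in BCDVA from Postop Week 3 or from Preoperative will be presented at each visit as categorical outcomes". No rule links a reference to a visit.

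The neighbouring analyses each name one reference. For uncorrected acuity (UCDVA), section 8.1.1 says "Change in UCDVA from Postop Week 3 will be presented at each visit as categorical outcomes". The intraocular pressure summary in 8.2.1 measures change from the preoperative value.

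The timing is clear. Section 7.4 places the first light treatment at the Week 3 visit: "Days 17 to 24 postop: Adjustment #1". Section 7.3.2.2 adds: "Protocol-required measurements should be completed prior to adjustment or lock-in treatments". Section 6.1 requires a cataract that reduces "best corrected distance visual acuity (BCDVA) to a level of 20/32 or worse with or without a glare source", and projected BCDVA "to be 20/20 or better after cataract removal and IOL implantation".

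The safety set in 8.1 is all eyes of consenting subjects in which "the procedure was attempted which is defined as the point at which the RxLAL makes contact with the eye". Section 5.2 lists the safety parameters as ocular adverse events and secondary surgical interventions; BCDVA comes under additional safety analyses.

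**The concern.** The two references answer different questions. Change from Week 3 isolates the period of light treatment. Change from Preoperative adds the gain from removing the cataract, and that gain can cancel a later loss in the same eye.

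The protocol treats such a loss as important. Section 9.2.5 warns that adjustment or lock-in may worsen vision. Under section 7.3.2.1, on a BCDVA loss "of 10 letters or more on an ETDRS (logMAR) chart, treatment should be delayed", unless the cause is known not to be retinal. A table that puts a loss of that size in the no-change band would be a poor safety display. As worded, a preoperative-only table would comply with the plan, and the choice could be made after the data are seen.

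**Working it through.** The plan gives no figure on this point to reproduce, so the check is how a given loss is classified under each reference.

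**Inputs.** The letter bands come from 8.2.1, and the entry level of 20/32 and projected 20/20 from 6.1. Three assumptions are not in the plan: 50 letters per 1.0 logMAR (5 per line), Week 3 BCDVA of 20/20, and a change under 5 letters counted as no change.

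**Formulas.** Let G be the letters gained from Preoperative to Week 3 and L the letters lost afterwards.

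- Change from Week 3 = −L
- Change from Preoperative = G − L
- G = 50 × log10(preoperative Snellen denominator / 20). This gives 4.8, 10.2, 15.1 and 24.9 letters for 20/25, 20/32, 20/40 and 20/63, rounded below to whole lines.

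From Week 3, L = 10 always reads as a 10–14 letter decrease, and L = 15 as a decrease of 15 or more. From Preoperative:

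| Preoperative BCDVA | G | L = 10 | L = 15 |
|---|---|---|---|
| 20/20 | 0 | −10: decrease 10–14 | −15: decrease 15 or more |
| 20/25 | 5 | −5: decrease 5–9 | −10: decrease 10–14 |
| 20/32 | 10 | 0: no change | −5: decrease 5–9 |
| 20/40 | 15 | +5: increase 5–9 | 0: no change |
| 20/63 | 25 | +15: increase 15 or more | +10: increase 10–14 |

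Preoperative 20/20 and 20/25 are possible because an eye may qualify on acuity under glare. Those eyes show little or no masking.

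**What the other promised BCDVA outputs would show.** Suppose 3 of 150 eyes (2%) fall from 20/20 to 20/40, a 15-letter loss. The mean score drops by 3 × 15 / 150 = 0.3 letters, which nobody would notice. The cumulative categories are more sensitive: the three eyes leave the 20/20, 20/25 and 20/32 rows. If three other eyes improve to 20/20 at the same time, the net change depends on where they started:

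| Improving eyes start at | 20/20 or better | 20/25 or better | 20/32 or better |
|---|---|---|---|
| (no improving eyes) | −3 | −3 | −3 |
| 20/25 | 0 | −3 | −3 |
| 20/32 | 0 | 0 | −3 |
| 20/40 or worse | 0 | 0 | 0 |

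An offset in the top row alone does not hide the loss. Full concealment needs all three improving eyes to start at 20/40 or worse.

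**Which reference can serve which visit.** Postop Day 1 and Week 1 precede Week 3, so a Week 3 reference gives no meaningful change there, and at Week 3 it gives zero by construction. An eye that the lens touched but that never reached Week 3 has only a preoperative value. One reference cannot cover every visit and every eye in the safety set; the two named references together can.

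**The case for a change.** The strongest case for a change is that the plan permits the weaker table. UCDVA and intraocular pressure each have one reference, and only the BCDVA table is left open. The appeal to early visits should not be pressed too far, since the UCDVA sentence also says each visit while naming Week 3 alone. The visit-by-assessment table is missing from the available text, so whether BCDVA is measured on Day 1 or at Week 1 cannot be confirmed. By-visit categories are group counts and never count eyes that lost 10 or 15 letters since Week 3. Three specific adverse event triggers in section 9.1 are redacted, so they cannot be relied on to catch such eyes. A clarifying sentence would cost almost nothing.

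Most of this stands as description: the rule is unwritten, and the change table is the only output described that would count within-eye loss. What does not stand is the step from there to likely harm. Week 3 is named, and named first, and it is already the UCDVA reference. Tabulating only Preoperative after light treatment means discarding it for no evident reason. Preoperative is also a legitimate reference for a safety measure that covers surgery, lens and light together, as the pressure summary shows. Individual losses have another route as well: section 8.2 presents all ocular adverse events, related or not, and section 9.2.1 requires documentation of those that arise from a test result.

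**Conclusion.** No change to the plan is needed. The wording leaves a selection rule unwritten, and analysts would fill it sensibly from two baselines the plan already names: either both tables, or Preoperative where no Week 3 value exists and Week 3 thereafter. Under either reading, a 10-letter loss since Week 3 appears as such at visits after the first adjustment.

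If the sponsor did tabulate Preoperative alone, a 10-letter loss would read as no change for an eye at 20/32 before surgery and as a gain at 20/40, under the stated assumptions. The number of such eyes cannot be estimated. The effect would be confined to one descriptive table in an exploratory study without a primary effectiveness endpoint. No test, sample size or stated decision depends on it. The conclusion rests on the ordinary reading of the sentence, not on the redacted adverse event triggers.

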#### Intraocular Pressure (IOP)

The IOP and change in IOP from preoperative will be summarized by mean, standard deviation, median, minimum and maximum. The number and percent of eyes reported with  $IOP \geq 25 \text{ mmHg}$  or an IOP increase of  $\geq 10 \text{ mmHg}$  from baseline will be provided at each visit.

#### Slit Lamp Examination and Fundus Examination Findings

The outcomes will be summarized descriptively by count and percent of eyes with each possible finding category.

## 9 ADVERSE EVENTS

If an adverse event (AE) occurs, the first concern will be the safety and welfare of the subject; treatment should be provided as appropriate for the event. During the study, the Investigator should appropriately treat and follow each AE until it resolves, stabilizes, or it is determined that further improvement is not expected.

### 9.1 ADVERSE EVENT DEFINITIONS

An adverse event (AE) is any untoward medical occurrence, unintended disease or injury, or untoward clinical signs (including abnormal laboratory findings) in subjects, users, or other persons, whether or not related to the investigational medical device.

Note 1 to entry: This definition includes events related to the investigational medical device or the comparator.

Note 2 to entry: This definition includes events related to the procedures involved.

Note 3 to entry: For users or other persons, this definition is restricted to events related to investigational medical devices.

The following may be considered normal events after cataract surgery and only need to be reported as AEs as specified:

- Iritis/cells/flare (if present after Postop Week 1 and greater than grade 1 (trace)) or (any iritis/cells/flare present at 6 Months Postop (3 Months Post Lock-In) of any grade)
- Corneal edema (if present after Postop Week 1 and greater than grade 1 (trace)) or (if present at 6 Months Postop (3 Months Post Lock-In) of any grade)
- Raised intraocular pressure (IOP) >10 mmHg above preoperative and greater than 25 mmHg (if present after Postop Week 1)

In addition, the specific following events should be reported as an AE:

- A [REDACTED] at any time after Postop Week 3.
- An [REDACTED] at any time after Postop Week 3.
- An [REDACTED] at the 6 Months Postop (3 Months Post Lock-In) visit.

### 9.2 SERIOUS ADVERSE EVENT DEFINITION

Serious Adverse Events (SAEs) are AEs that lead to:

- death
- a serious deterioration in the health of the subject that:
  - results in a life-threatening illness or injury
  - results in a permanent impairment of a body structure or function (e.g., blindness)
  - requires in-subject hospitalization or prolongation of existing hospitalization

- results in medical or surgical intervention to prevent permanent impairment to a body structure or a body function
- fetal distress, fetal death, or a congenital abnormality or birth defect
- a potentially sight-threatening condition
- or is another important medical event.

### 9.2.1 IDENTIFICATION AND COLLECTION

Identification and collection of an AE begins after informed consent has been obtained and documented. Standard sources of identifying AEs include:

- direct observation by the Investigator or study team member
- asking the study participant a specific question (e.g., “Since your last visit, have you experienced any problems with your eyes or vision?”)
- unsolicited volunteering of information by the study participant (e.g., “Doctor, I have had numerous headaches since I started using this lens.”)

Ocular AEs and SAEs and systemic SAEs observed or elicited by the Investigator, reported by the subject, or resulting from a test result, etc., occurring during the clinical investigation must be documented. During the study, the Investigator should treat the study subject as appropriate to ensure his/her safety and welfare. Refer to Section 7.7.1 for additional information pertaining to ongoing AEs at subject exit.

Pre-existing conditions will not be considered AE/SAEs but will be collected at the Preoperative Visit as medical history. A worsening of a pre-existing condition during the study should be documented as an AE and evaluated accordingly.

Hospitalization is a criterion for assessment of seriousness. Hospitalization in the absence of a medical AE is not in itself an AE. For example, the following reports of hospitalization without a medical AE should not be considered either an SAE or an AE:

- Planned hospitalization for a pre-existing condition without serious deterioration in health (e.g., planned knee replacement surgery)
- Social admission (e.g., subject has no place to sleep)
- Administrative admission (e.g., for yearly physical exam or elective procedures not related to the study)
- Optional admission not associated with a precipitation medical AE (e.g., for elective cosmetic surgery)

### 9.2.2 EVALUATIONS

When evaluating AEs, the Investigator must determine if the event is serious, assess the severity of symptoms, the relationship of the event to the device or study protocol, using the following guidelines:

## 1. Severity

**Mild:** subject awareness of a sign or symptom that is easily tolerated, requires no treatment, and does not interfere with subject's daily activities

**Moderate:** subject awareness of a sign or symptom which may be a low level of concern to the subject and may interfere with daily activities, but can be relieved by simple therapeutic care

**Severe:** a sign or symptom that interrupts the subject's daily activity and requires systemic therapy or other treatment

## 2. Relationship (Causality) to Study Device or Study Protocol

**Related:** There is at least a reasonable possibility that the AE/SAE is related to the study device or study protocol. Reasonable possibility means that there is evidence to suggest a causal relationship between the study device or study protocol and the AE.

**Unrelated:** There is little or no reasonable possibility that the AE/SAE is related to the study device or study protocol. This assessment implies that the AE/SAE has little or no temporal relationship to the study device and/or a more likely or certain alternative etiology exists.

### 9.2.3 SAE REPORTING

The site should report any event to the Sponsor and its representative in an expedited manner if it meets the criteria for an SAE and/or is an IOL explant from a study eye. Expedited reporting is calling or e-mailing the Sponsor and its representative within 48 hours of becoming aware of the event. When reporting an SAE to the Sponsor and/or its representative, the site should forward any supporting documents along with the SAE Report Form to the Sponsor and its designee within 5 days of the initial communication. Sites must also report the SAE to the reviewing Ethics Committee per its reporting procedures.

### 9.2.4 PREGNANCY

During the study, all female subjects of childbearing potential should be instructed to contact the investigator immediately if they suspect they might be pregnant (e.g., missed or late menstrual period). Female subjects who become pregnant during the study will be followed until completion of pregnancy. Every effort will be made to obtain the health status of the mother and infant or fetus (in cases of miscarriage or therapeutic abortion) at term. Pregnancy itself is not considered an AE.

All confirmed pregnancies must be immediately reported to the Sponsor within 48 hours of the investigator's awareness of the pregnancy.

### 9.2.5 POTENTIAL ADVERSE EVENTS

The following have been identified as potential adverse events for all cataract surgeries including the RxLAL. Please notify the Sponsor regarding any events that may be occurring more frequently than your customary rates, or more frequently than expected at your site.

Infection, inflammation, hypopyon, endophthalmitis, infectious keratitis, hyphema, retinal detachment or other retinal problems including cystoid macular edema and epiretinal membranes, toxic anterior segment syndrome, glaucoma, corneal endothelial damage, corneal edema which may require correction with a corneal transplant, lens dislocation out of the posterior chamber, pupillary block, striation on the lens with or without visual sequelae, iritis, synechiae, ptosis, wound leak, flat anterior chamber, increased astigmatism, rupture of the capsule, iris prolapse, vitreous in the anterior chamber, and retained pieces of the lens in the eye. These adverse events may result in total loss of vision or the loss of an eye.

Secondary surgery may be required after the cataract surgery to treat surgical complications. Additionally, a posterior capsulotomy may be required to treat posterior capsular haze after the cataract surgery. Visual problems after cataract surgery may include halos, glare, ghost images, and/or double vision. These and other complications may result in permanent poor vision.

Additional specific risks of the RxLAL include:

The RxLAL must be implanted following specific surgical procedures. If these procedures are not followed by the surgeon, the lens may become scratched or improperly placed in the eye and may need to be explanted prior to light treatments. In order to perform the lens adjustment or the lens lock-in procedures, the subject's pupil needs to be adequately dilated. If this cannot be accomplished for any reason, additional eye drops, injections into the eye, or surgery may need to be utilized to adequately dilate the pupil. If the pupil cannot be adequately dilated after these types of treatments, the RxLAL may need to be explanted. An unpredicted change in vision can occur resulting from ocular exposure to daylight or any other UV source before the RxLAL is locked-in. The light treatments may not improve vision and/or manifest refraction, and the adjustment/lock-in procedure may make vision worse, such that it may be necessary to remove and replace the RxLAL. Vision loss may be permanent and may not be improved by replacing the RxLAL. There is a potential risk for UV-induced damage to the eye, including the cornea and retina, which may be permanent. UV light can sometimes cause a reactivation of previous herpes virus infection in the eye. A reactivation of herpes virus can cause scarring of the cornea, blurred vision, eye pain, extreme light sensitivity, permanent loss of vision, and possible need for corneal transplant. Temporary or persistent erythropsia and/or temporary or persistent color vision deficiency may occur. Corneal dryness and corneal abrasions from the lens used for adjustment and lock-in can occur. After the lens adjustment(s) or after the lens lock-in procedures, discomfort, itching and light sensitivity may occur. In cases where a spherocylinder adjustment is performed, it is possible that visual disturbances may occur if the IOL rotates or if the correction is not performed on the correct axis of astigmatism.

